7.2.4 Time since Asthma diagnosis

In asthmatic patients, the number of years since diagnosis will be obtained as the difference between year of study visit and year of Asthma diagnosis (+1).

Document: \\bcnfs02\general\Hdmgener\MEDICAL AFFAIRS 28.02.2017 actualizada\8. SRO ESTUDIOS\RESPIRATORIO\1237-0070 NIS OPTI\11 - Clinical Trial Report\SAP\SAP - V 1.0\SAP OPTI version1.0 29052019.docx

Author:

Version Number: 1.0

Version Date: [29MAY2019]

Template No.: RWI_TP_BIOS0013 Revision 1

Reference: RWI_WI_BIOS0015

Effective Date: 15Jun2018

Copyright © 2018 All rights reserved. The contents of this document are confidential and proprietary to Holdings Inc. and its subsidiaries. Unauthorized use, disclosure or reproduction is strictly prohibited.

7.2.5 Spirometric values

Spirometric data are collected directly from clinical records. However, Predicted FEV₁/FVC pre and post bronchodilator and change in FEV₁ will be calculated using the formulas:

$$\text{Predicted FEV1 (L)} = 100 \times \text{FEV1 (L)} / \text{FEV1 (\%)}$$

$$\text{Predicted FVC (L)} = 100 \times \text{FVC (L)} / \text{FVC (\%)}$$

$$\text{Change (L) in FEV1} = \text{FEV1 Post (L)} - \text{FEV1 Pre (L)}$$

$$\text{Percentage (1) of change in FEV1 (\%)} = 100 \times [\text{FEV1 Post (L)} - \text{FEV1 Pre (L)}] / \text{Predicted FEV1 (L)}$$

$$\text{Percentage (2) of change in FEV1 (\%)} = 100 \times [\text{FEV1 Post (L)} - \text{FEV1 Pre (L)}] / \text{Predicted FEV1 Pre (L)}$$

7.2.6 Number of exacerbations

7.2.6.1 Number of total exacerbations

The number of exacerbations (mild, moderate and severe) in the last two years will be the number of exacerbations registered in section 8 of CRF, whose date of exacerbation is included in the last 2 years or 730.50 days (365.25x2) before the study visit.

The number of exacerbations in the last year will be the number of exacerbations registered in section 8 of CRF, whose date of exacerbation is included in the last 365 days before the study visit.

In both cases, the number of exacerbations will be assumed as zero when “without exacerbation in the last 2 years” is ticked.

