An exacerbation is defined as an acute worsening of respiratory symptoms that result in additional therapy (6):

- Moderate exacerbation: increase in, or new onset of, ≥ 2 respiratory symptoms (cough, sputum, dyspnea, wheezing, chest tightness) with ≥ 1 symptom lasting ≥ 3 days and leading the patient's attending physician to initiate treatment with systemic corticosteroids and/or antibiotics.
- Severe exacerbation: increase in or new onset of ≥ 2 respiratory symptoms (cough, sputum, dyspnoea, wheezing, chest tightness) with ≥ 1 symptom lasting ≥ 3 days and leading to patient's hospitalization.

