7.2.6.2 Number of severe exacerbations

The number of severe exacerbations in the last two years will be the number of exacerbations requiring hospitalization, registered in section 8 of CRF, whose date of exacerbation is included in the last 2 years or 730.5 days (365.25x2) before the study visit.

The number of severe exacerbations in the last year will be the number of exacerbations registered in section 8 of CRF, whose date of exacerbation is included in the last 365 days before the study visit and required hospitalization.

In both cases, the number of severe exacerbations will be assumed as zero when “without exacerbation in the last 2 years” is ticked.

Document: \\bcnfs02\general\Hdmgener\MEDICAL AFFAIRS 28.02.2017 actualizada\8. SRO ESTUDIOS\RESPIRATORIO\1237-0070 NIS OPTI\11 - Clinical Trial Report\SAP\SAP - V 1.0\SAP OPTI version1.0 29052019.docx

Author:

Version Number: 1.0

Version Date: [29MAY2019]

Template No.: RWI_TP_BIOS0013 Revision 1

Reference: RWI_WI_BIOS0015

Effective Date: 15Jun2018

Copyright © 2018 All rights reserved. The contents of this document are confidential and proprietary to Holdings Inc. and its subsidiaries. Unauthorized use, disclosure or reproduction is strictly prohibited.

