7.2.11 Risk stratification

Patients will be classified according to their risk based on GesEPOC 2017 Spanish guideline:

- Low risk:
 - FEV₁(%) post-bronchodilation ≥ 50% and,
 - mMRC 0-2, and
 - 0 or 1 exacerbation in the last year, and
 - without hospitalization in the last year.
- High risk:
 - FEV₁(%) post-bronchodilation <50% or,
 - mMRC > 2 or mMRC = 2 with treatment or,
 - 2 or more exacerbation in the last year or,
 - 1 or more exacerbation with hospitalization in the last year.

Document: \\bcnfs02\general\Hdmgener\MEDICAL AFFAIRS 28.02.2017 actualizada\8. SRO ESTUDIOS\RESPIRATORIO\1237-0070 NIS OPTI\11 - Clinical Trial Report\SAP\SAP - V 1.0\SAP OPTI version1.0 29052019.docx

Author: Version Number: 1.0

Version Date: [29MAY2019]

Template No.: RWI_TP_BIOS0013 Revision 1

Reference: RWI_WI_BIOS0015

Effective Date: 15Jun2018

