7.2.12 Gold 2019 Classification

According to GOLD 2019 classification, four different types of patients will be considered:

- Patient A:
 - 0 or 1 exacerbations (not leading to hospital admission) and,
 - mMRC 0-1 and CAT < 10
- Patient B:
 - 0 or 1 exacerbations (not leading to hospital admission), and
 - mMRC ≥ 2 or CAT ≥ 10
- Patient C:
 - ≥ 2 exacerbations or ≥ 1 exacerbation leading to hospital admission, and
 - mMRC 0-1 and CAT < 10.
- Patient D:
 - ≥ 2 exacerbations or any ≥ 1 exacerbation leading to hospital admission, and
 - mMRC ≥ 2 or CAT ≥ 10 .

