16.1.3.2 Inadequate use of ICS

As a part of main analysis, inadequate use of ICS will be presented as in the previous section 16.1.3.1. Current treatment with ICS. This analysis will be presented only for patients without exacerbations in the previous year. This cohort will be used because only patients without exacerbations can receive ICS without requiring it, which is, making an inappropriate use of the treatment.

Document: \\bcnfs02\general\Hdmgener\MEDICAL AFFAIRS 28.02.2017 actualizada\8. SRO ESTUDIOS\RESPIRATORIO\1237-0070 NIS OPT\11 - Clinical Trial Report\SAP\SAP - V 1.0\SAP OPTI version1.0 29052019.docx

Author:

Version Number: 1.0

Version Date: [29MAY2019]

Template No.: RWI_TP_BIOS0013 Revision 1

Reference: RWI_WI_BIOS0015

Effective Date: 15Jun2018

Copyright © 2018 All rights reserved. The contents of this document are confidential and proprietary to Holdings Inc. and its subsidiaries. Unauthorized use, disclosure or reproduction is strictly prohibited.

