20.3 Endpoints

20.3.1 ICS treatment

Table 24. Current treatment on ICS according to the absence or presence of moderate/severe exacerbations in the year prior to the study visit.

ICS treatment	Moderate/severe Exacerbations in the previous year		Total
	No	Yes	
Total patients	N (100%)	N (100%)	N (100%)
Currently non treated with ICS	XXX (XX.X%) [95%CI: XX.X%-XX.X]	XXX (XX.X%) [95%CI: XX.X%-XX.X]	XXX (XX.X%) [95%CI: XX.X%-XX.X]
Currently treated with ICS	XXX (XX.X%) [95%CI: XX.X%-XX.X]	XXX (XX.X%) [95%CI: XX.X%-XX.X]	XXX (XX.X%) [95%CI: XX.X%-XX.X]

*Note: Percentages will be column percentages. Each percentage will correspond to percentage of patients currently treated with ICS, according to the presence of moderate/severe exacerbations in the previous year.

Table 25. Inadequate use of ICS (use of ICS without moderate/severe exacerbations in the previous year) according to clinical and demographic factors (univariate logistic regression analysis)

Variable	Category	Inadequate use of ICS	Odds-Ratio (OR)	p-value
Age	Cont (1 year)	n/N (%)		
Age (cat)	40-49 years	n/N (%)	(ref)	
	50-59 years	n/N (%)		
	60-69 years	n/N (%)		
	70-79 years	n/N (%)		
	80+ years	n/N (%)		

Document: \\bcnfs02\general\Hdmgener\MEDICAL AFFAIRS 28.02.2017 actualizada\8. SRO ESTUDIOS\RESPIRATORIO\1237-0070 NIS OPTI\11 - Clinical Trial Report\SAP\SAP - V 1.0\SAP OPTI version1.0 29052019.docx

Author:

Version Number: 1.0

Version Date: [29MAY2019]

Template No.: RWI_TP_BIOS0013 Revision 1

Reference: RWI_WI_BIOS0015

Effective Date: 15Jun2018

Copyright © 2018 All rights reserved. The contents of this document are confidential and proprietary to Holdings Inc. and its subsidiaries. Unauthorized use, disclosure or reproduction is strictly prohibited.

Variable	Category	Inadequate use of ICS	Odds-Ratio (OR)	p-value
Gender	Male Female		(ref)	
BMI cat	Underweight: BMI< 18.5 kg/m ² Normal weight: 18.5 kg/m ² ≤ BMI≤ 25 kg/m ² Overweight: 25 kg/m ² < BMI≤ 30 kg/m ² Obese: 30 kg/m ² <BMI≤ 35 kg/m ² Severely Obese: BMI> 35 kg/m ²		(ref)	
Smoking habit	Non-smoker Smoker Ex-smoker		(ref)	
History of asthma	No Yes		(ref)	
History of atopy	No Yes		(ref)	
BODEx Index (cat)	Class I Mild: BODEx 0-2 points Class II Moderate: BODEx 3-4 points Class III Serious: BODEx 5-6 points Class IV Very serious: BODEx 7-9 points		(ref)	
COTE Index (cat)	Low risk: COTE index <4 points High risk: COTE index ≥ 4 points.		(ref)	
Time since COPD diagnosis (cat)	0-2 years >2-5 years >5 years		(ref)	

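### SAP 7.2.6 derives no moderate-to-severe exacerbation count, the GesEPOC risk, GOLD A-D and adherence rules do not say which count they use, and the cohort text of 16.1.3.2 conflicts with its tables

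*SAP*

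**What the plan says.** **Counts derived.** SAP 7.2.6.1 opens with "The number of exacerbations (mild, moderate and severe) in the last two years". For one year it says "The number of exacerbations in the last year will be the number of exacerbations registered in section 8 of CRF", limited to the last 365 days and with no severity filter. SAP 7.2.6.2 adds the severe count: "The number of severe exacerbations in the last two years will be the number of exacerbations requiring hospitalization", with a matching one-year version. No third count follows.

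**Where moderate/severe is required.** The primary endpoint (SAP 16.1, 16.1.3, 16.1.3.1), section 16.2.2 and Tables 5, 11, 24, 31, 32 and 35 all refer to moderate/severe exacerbations.

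**Rules that name no severity.** The high-risk class in SAP 7.2.11 includes "2 or more exacerbation in the last year or". Groups A and B in SAP 7.2.12 require "0 or 1 exacerbations (not leading to hospital admission", with no look-back period. SAP 16.2.5 and Table 38 split patients on the same 0-1 versus 2-or-more wording, over the last year.

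**Inadequate-use cohort.** The text of SAP 16.1.3.2 says "This analysis will be presented only for patients without exacerbations in the previous year". The title of Table 25 reads "Inadequate use of ICS (use of ICS without moderate/severe exacerbations in the previous year". Tables 5, 26 and 27 carry the same moderate/severe qualifier.

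**Protocol.** Section 9.3.2.2 says "An exacerbation is defined as an acute worsening of respiratory symptoms that result in additional therapy" and then describes two grades, moderate (systemic corticosteroids and/or antibiotics) and severe (hospitalisation). SAP 4.6 states that no protocol definition has been changed.

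**The concern.** A programmer working from the SAP has no rule for the count behind the primary endpoint. For the risk class, the GOLD groups and the adherence strata, the only derivation without a severity limit is 7.2.6.1, and SAP 11.1 sends the reader to 7.2 for derived variables. Using it would let two mild episodes put a patient at high risk, in group C or D, and in the upper adherence stratum. The SAP uses the word mild without defining it.

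The effect would spread. The risk class is one of the two conditions for ICS being indicated under SAP 7.2.14, so it feeds the adherence result. GOLD groups and the number of exacerbations in the previous year are candidate covariates in the logistic model of 16.1.3.1. In the inadequate-use analysis, a patient whose only episode last year was mild is excluded by the text of 16.1.3.2 but counted as event-free by its tables.

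**Working it through.** **The plan's own figures.** SAP 4.2 takes 66% non-exacerbators, 61% of them on ICS, N = 900 and 10% drop-out.
- 0.66 × 0.61 = 0.403, stated as approximately 40%.
- 0.40 ± 1.96 × √(0.40 × 0.60 / 900) = 0.40 ± 0.032, i.e. 36.8% to 43.2%, as stated.
- 900 / 0.90 = 1,000, as stated.

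All three reproduce. This point disputes none of them.

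**The rules side by side.**

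| Place in SAP | Severity named | Window named |
|---|---|---|
| 7.2.6.1 total count | all, mild included | 365 and 730.5 days |
| 7.2.6.2 severe count | hospitalised | 365 and 730.5 days |
| 7.2.11 GesEPOC risk | none | last year |
| 7.2.12 GOLD A-D | none | none |
| 16.2.5, Table 38 strata | none | last year |
| 16.1.3.1 main variable | moderate/severe | 365 days |
| 16.1.3.2 cohort text | none | previous year |
| Tables 5, 25-27 | moderate/severe | previous year |
| 16.2.1 two-year analysis | moderate/severe | 2×365 days |

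The last row also differs from the 730.5 days of 7.2.6.

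**Illustration of size.** The 66% with no event is the SAP's figure. The rate m of mild episodes per year, their independence of moderate/severe episodes, and the shape of the moderate/severe distribution are assumptions. Let p0 = 0.66 and p1 be the probabilities of zero and one moderate/severe episode in the year. Three shapes fix p0 at 0.66:
- Poisson, mean 0.416: p1 = 0.274
- Negative binomial, size 1, mean 0.515: p1 = 0.224
- Negative binomial, size 0.5, mean 0.648: p1 = 0.186

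Adding a Poisson number of mild episodes with mean m:
- P(none) = p0·e^(−m)
- P(one) = e^(−m)·(p1 + p0·m)
- P(two or more) = 1 − P(none) − P(one)

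Example, Poisson shape, m = 0.25, e^(−0.25) = 0.779:
- P(none) = 0.66 × 0.779 = 0.514
- P(one) = 0.779 × (0.274 + 0.165) = 0.342
- P(two or more) = 0.144, against 0.066 without mild episodes, so 7.8% of patients cross

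| m (assumed) | None in year | Of 900 | Two or more: Poisson / NB 1 / NB 0.5 | Cross to two or more |
|---|---|---|---|---|
| 0 | 66.0% | 594 | 6.6 / 11.6 / 15.4% | 0 |
| 0.1 | 59.7% | 537 | 9.5 / 14.0 / 17.5% | 2.1-2.9% (19-26 of 900) |
| 0.25 | 51.4% | 463 | 14.4 / 18.3 / 21.2% | 5.9-7.8% (53-70) |
| 0.5 | 40.0% | 360 | 23.3 / 26.3 / 28.7% | 13.3-16.7% (120-151) |

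The third column is the cohort that the text of 16.1.3.2 would leave, read literally, against 594 under the tables. The last column makes no allowance for patients already classed by a hospitalised episode or, for risk, by FEV₁ or mMRC.

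**The case against.** - **No rule cites 7.2.6.1.** That section is headed as the total count, Table 11 keeps total, moderate/severe and severe apart, and the adherence strata repeat the protocol's own unqualified wording. A reader might infer that patients will be classified on events outside the protocol definition. The documents do not say so; it follows only if 7.2.6.1 is applied. This stands.
- **Mild episodes are not expressly excluded by the protocol.** Its abstract and section 7 also describe an exacerbation as sustained deterioration of symptoms, with no therapy requirement. Section 9.3.2.2 lists no mild grade but does not rule one out. Which severities the GesEPOC and GOLD guidelines count cannot be seen here. This also stands, and is a reason for the SAP to name its count.
- **The cohort is qualified elsewhere.** Section 16.1.3.2 refers back to 16.1.3.1, where the variable is moderate/severe, and the tables agree with that. The likely intention is therefore clear, but the sentence that selects the cohort still says otherwise.
- **High risk alone does not make ICS indicated.** SAP 7.2.14 also requires an exacerbator or mixed phenotype, which Protocol 9.3.3 takes from charts. A non-exacerbator with two mild episodes would be high risk yet still not ICS-indicated. GOLD A-D does not enter that rule, and the 16.2.5 strata only define table columns. A reader might infer that mild episodes by themselves make ICS indicated; they do not.
- **The size rests on assumed rates.** Correct; if section 8 of the CRF holds few mild episodes, the shift is close to nil.

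**Conclusion.** The concern holds as a gap and an inconsistency in the SAP. The moderate-to-severe count has no derivation, three sets of classification rules do not name their count, GOLD A-D has no window, and the text of 16.1.3.2 contradicts Tables 5 and 25-27. This is more than missing detail, because the one derivation that fits the unqualified wording would change classifications.

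It does not show that the primary endpoint has been redefined. The endpoint is explicitly moderate/severe throughout; what it lacks is the derivation. Nor does it affect the study size.

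The amount of reclassification cannot be known from the documents. It runs from none, through about 2-3% of patients crossing to two or more at an assumed 0.1 mild episodes per year, to 6-8% at 0.25 and 13-17% at 0.5, given 66% event-free and independent mild episodes.

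**What to change.** 1. Add to SAP 7.2.6 a derivation of moderate-to-severe exacerbations using the Protocol 9.3.2.2 definition, for the one-year (365-day) and two-year windows. Choose one two-year length, since 7.2.6 has 730.5 days and 16.2.1 has 2×365.
2. Name that count and the 365-day window in 7.2.11, 7.2.12, 16.2.5 and Table 38. If the sponsor intends another count for a guideline class, state it there and declare it in 4.6.
3. In 16.1.3.2, restrict the cohort to patients without moderate/severe exacerbations, to match Tables 5 and 25-27.
4. Keep the total count for the descriptive rows labelled total.

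The cost is SAP text and minor programming, provided the eCRF allows each episode to be graded. Hospitalisation per episode is supported by 7.2.6.2. Treatment per episode is only inferred from Tables 11 and 12, and Protocol 9.3.3 lists exacerbation details and antibiotic/corticosteroid history as separate variables, so this should be confirmed first.

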7.2.6.2 Number of severe exacerbations

The number of severe exacerbations in the last two years will be the number of exacerbations requiring hospitalization, registered in section 8 of CRF, whose date of exacerbation is included in the last 2 years or 730.5 days (365.25x2) before the study visit.

The number of severe exacerbations in the last year will be the number of exacerbations registered in section 8 of CRF, whose date of exacerbation is included in the last 365 days before the study visit and required hospitalization.

In both cases, the number of severe exacerbations will be assumed as zero when “without exacerbation in the last 2 years” is ticked.

Document: \\bcnfs02\general\Hdmgener\MEDICAL AFFAIRS 28.02.2017 actualizada\8. SRO ESTUDIOS\RESPIRATORIO\1237-0070 NIS OPTI\11 - Clinical Trial Report\SAP\SAP - V 1.0\SAP OPTI version1.0 29052019.docx

Author:

Version Number: 1.0

Version Date: [29MAY2019]

Template No.: RWI_TP_BIOS0013 Revision 1

Reference: RWI_WI_BIOS0015

Effective Date: 15Jun2018

Copyright © 2018 All rights reserved. The contents of this document are confidential and proprietary to Holdings Inc. and its subsidiaries. Unauthorized use, disclosure or reproduction is strictly prohibited.

7.2.7 Laboratory values

7.2.7.1 *Eosinophils*

Eosinophils will be categorized in two categories (for each unit) (Celli 2017) (GOLD 2019):

- If eosinophils are in %: $<2\%$ and $\geq 2\%$
- If eosinophils are in cells/ μl : <100 , $100-299$ and ≥ 300 .

7.2.7.2 *Immunoglobulin E*

Immunoglobulin E (IgE) levels will be categorized according to these values, included in the Spanish Asthma guidelines (GEMA) and ACO (Cosio et al. 2016):

- ≤ 100 UI/ml
- > 100 UI/ml

7.2.8 GOLD 2019

To determine the severity of all subjects with COPD (independently of FEV₁/FVC post-bronchodilation obtained), patients will be categorized into four levels, according to these criteria:

- Gold 1 (mild): FEV₁ (%) $\geq 80\%$ predicted.
- Gold 2 (Moderate): $50\% \leq \text{FEV}_1 (\%) < 80\%$ predicted.
- Gold 3 (Severe): $30\% \leq \text{FEV}_1 (\%) < 50\%$ predicted.
- Gold 4 (Very serious): FEV₁ (%) $< 30\%$ predicted.

In case the number of GOLD 4 subjects was less than 10, these will be grouped with the GOLD 3 subjects, forming a single category (GOLD 3-4).

7.2.9 BODEx Index

The BODEx index includes the body mass index (BMI), the degree of dyspnea measured with the mMRC scale, the pulmonary function measured with the FEV₁ (%) post-bronchodilation and the

Document: \\bcnfs02\general\Hdmgener\MEDICAL AFFAIRS 28.02.2017 actualizada\8. SRO ESTUDIOS\RESPIRATORIO\1237-0070 NIS OPTI\11 - Clinical Trial Report\SAP\SAP - V 1.0\SAP OPTI version1.0 29052019.docx

Author:

Version Number: 1.0

Version Date: [29MAY2019]

Template No.: RWI_TP_BIOS0013 Revision 1

Reference: RWI_WI_BIOS0015

Effective Date: 15Jun2018

Copyright © 2018 All rights reserved. The contents of this document are confidential and proprietary to Holdings Inc. and its subsidiaries. Unauthorized use, disclosure or reproduction is strictly prohibited.

number of severe exacerbations (only visits to hospital emergencies and admissions are included). It is a continuous variable with a range from 0 to 9 points.

Table A: Calculation of the BODEx Index for prognostic approach to COPD.

	Variables	Score			
		0	1	2	3
B	BMI (kg/m2)	>21	≤21		
O	FEV ₁ (%)	≥65	50-64	36-49	≤35
D	Dyspnea (mMRC)*	0-1	2	3	4
Ex	Severe Exacerbations)	0	1-2	≥3	

Propuesto por (Soler-Cataluna et al. 2009)

Taking into account the score obtained in the BODEX index, they can be grouped into the following categories:

- Class I Mild: BODEx 0-2 points
- Class II Moderate: BODEx 3-4 points
- Class III Serious: BODEx 5-6 points
- Class IV Very serious: BODEx 7-9 points

7.2.10 COTE Index

The COTE comorbidity index was constructed from the 12 comorbidities that were associated with a statistically significant risk of death (Divo et al. 2012). Thus, comorbidities such as hypertension and hypercholesterolemia, which are very frequent in patients with COPD, would not be associated with higher mortality, while others would be, such as cancer (particularly lung, esophagus, pancreas and breast), anxiety, liver cirrhosis, atrial fibrillation, diabetes, pulmonary fibrosis, heart failure, gastroduodenal ulcer and coronary heart disease.

The sum of the points aims to capture the individual or combination of diseases that affect each patient. The total score ranges between 0 and 25 points. An increase of 1 point in the COTE index is associated with an increased risk of death from episodes related to COPD and not related to COPD.

Document: \\bcnfs02\general\Hdmgener\MEDICAL AFFAIRS 28.02.2017 actualizada\8. SRO ESTUDIOS\RESPIRATORIO\1237-0070 NIS OPTI\11 - Clinical Trial Report\SAP\SAP - V 1.0\SAP OPTI version1.0 29052019.docx

Author: _____ Version Number: 1.0
 Version Date: [29MAY2019]

Template No.: RWI_TP_BIOS0013 Revision 1 Reference: RWI_WI_BIOS0015

Effective Date: 15Jun2018

Table B: Comorbidities associated with mortality and the COTE index

Disease	Points
Lung, esophagus, pancreas or breast cancer	6
Pulmonary fibrosis	2
Auricular Fibrillation / flutter	2
Congestive heart failure	1
Coronary artery disease	1
Gastroduodenal ulcer	1
Liver cirrhosis	2
Diabetic neuropathy	2
Anxiety	6
All other cancers	2
Total score	∑ (sum of all points)

The COTE index will also be described according to the mortality risk at this cut-off point:

- Low risk mortality: COTE index <4 points
- High risk mortality: COTE index ≥ 4 points.

7.2.11 Risk stratification

Patients will be classified according to their risk based on GesEPOC 2017 Spanish guideline:

- Low risk:
 - FEV₁(%) post-bronchodilation ≥ 50% and,
 - mMRC 0-2, and
 - 0 or 1 exacerbation in the last year, and
 - without hospitalization in the last year.
- High risk:
 - FEV₁(%) post-bronchodilation <50% or,
 - mMRC > 2 or mMRC = 2 with treatment or,
 - 2 or more exacerbation in the last year or,
 - 1 or more exacerbation with hospitalization in the last year.

Document: \\bcnfs02\general\Hdmgener\MEDICAL AFFAIRS 28.02.2017 actualizada\8. SRO ESTUDIOS\RESPIRATORIO\1237-0070 NIS OPTI\11 - Clinical Trial Report\SAP\SAP - V 1.0\SAP OPTI version1.0 29052019.docx

Author: Version Number: 1.0

Version Date: [29MAY2019]

Template No.: RWI_TP_BIOS0013 Revision 1

Reference: RWI_WI_BIOS0015

Effective Date: 15Jun2018

